Surgery and dismissal: Participants will be randomized 1:1 to one of the 2 groups upon dismissal from the hospital after bilateral oophorectomy: standard dose estradiol, (including dosing dictated by personal medical history) or titrated dose estradiol therapy. Women with an intact uterus will also be prescribed a progestogen for endometrial protection. The preferred progestogen will be oral micronized progesterone, given as oral dose 100 mg daily or 200 mg cyclically during the first 12 days of month. Women belonging to the titrated dose ET group will initially be dismissed on the standard 100 mcg transdermal estradiol patch. They will have their estradiol levels checked once every 3-4 weeks (clinical visits overseen by our MD investigators in the Menopause and Women's Sexual Health Clinic) and the estradiol dose accordingly titrated until they reach the desired goal of an estradiol level of 80-120 pg/ml. If women in the standard dose group report residual symptoms despite treatment, we will offer titration to a higher dose of ET. Women intolerant of the estradiol patch will be treated with oral estradiol at an equivalent dose. Women with intolerance/side-effects/abnormal uterine bleeding with progesterone will be offered an alternative progestogen for uterine protection. Clinical care of the subjects will be overseen by clinical care providers in the Menopause and Women's Sexual Health Clinic.

The study is designed to have active study participants on varying hormone replacement after oophorectomy as dictated by their clinical needs.

Post-operative Study Visit at 6 Months: The same protocol will be followed as the baseline study day protocol above except we will not check glucose, lipids and insulin levels, and DXA scan will not be performed, as it will take longer than 6 months to see changes in these measures. Blood samples drawn for levels of estradiol and estrone will ideally be drawn on the second day after application of a new patch.

Post-operative Study Visit at 12 Months: Subjects will report to the clinical research and trials unit (CRTU), and the same protocol will be followed as that of the baseline study day visit. All blood samples will be drawn in

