the same way as done for the baseline visit. A 24-hour urine sample will be collected again in a mail-in kit as described above. Participants on any kind of exogenous glucocorticoid therapy will be excluded from this part of the study. Urine samples will be aliquoted and stored as a part of the IRB # 13-005838 biobank. Urine steroid profiling will be performed in batches in the ICL lab.

Time controls will complete baseline, 6 month, and 12 month study visits.

Participant Retention: All participants will be remunerated up to \$300. Participants will be remunerated \$100 for each of the following visits: baseline, six months and twelve months. If a participant refuse the cardiovascular testing, and chooses the option to complete the blood-work, questionnaires and DXA scan only, they will be remunerated \$50 for each of the following visits: baseline, six months and twelve months. Amounts will be prorated according to the visits the participant completes. In addition, participants will be provided with Mayo parking vouchers for the time they are onsite for study visits. For CRTU visits, participants will be given six-hour vouchers, and for other visits participants would be given 2 hour parking vouchers. After the long visits in the CRTU, which requires fasting for 8 hours, participants will be provided a meal.

Statistics (prepared in collaboration with [name], Ph.D.): For the proposed investigation, women 21-45 years of age undergoing bilateral oophorectomy will be randomized to one of two groups, based on the regimen of estradiol replacement therapy (standard versus titrated). In addition to estradiol, patients who do not undergo hysterectomy will receive a progestogen as clinically indicated. A randomization schedule will be generated by the Section of Biostatistics using varied blocked randomization to attain an equal number of women assigned to each treatment group. Covariates not balanced through randomization, such as additional hormone use in patients with hysterectomy, will be accounted for in analysis. For all aims, the primary analyses will be performed using intention to treat with **estradiol dosing regimen** as the *treatment group variable* and secondary analyses will be performed using the **serum estradiol concentration (E2)** as a *continuous explanatory variable*.

Statistical Analysis:

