Aims 1 and 3: We will first perform cluster analysis among the variables to identify set of variables that are highly correlated, and regression analysis to identify the dependency between the outcome variable and its covariate. We will also perform a multivariable regression analysis taking into account all the covariates and applying penalized methods such as least absolute shrinkage selection operator (lasso) [17] for covariate selection.

Aim 2: We will plot the data to identify the patterns between the outcome variable and the covariates. We will then fit a mixed-effects model with two fixed effects parameters, the intercept and the slope of the linear trend for the population, and two random effects for each participant, i.e., the deviations in intercept and slope of that participant's time trend from the population values.

Power calculation: The analysis of the 12 month outcomes will be considered the primary analysis, with analyses of the earlier time point used to supplement the primary findings. In all cases, distributional assumptions will be assessed with transformations or non-parametric methods used as appropriate. When the direction of a difference is hypothesized a priori (e.g. women receiving the lower dose of estradiol will have poorer endothelial vasodilator function) a one-tailed test will be used; if the direction is not stated a two-tailed test will be used.

Sample-size/statistical power considerations: In general, a sample-size of N=25 per group will provide statistical power (one-tailed, alpha=0.05) of 82% to detect a difference between groups of 0.75 standard deviation units. Therefore, although preliminary data are not available for each aim and the statistical power will differ for the multiple facets of each aim, we believe that a sample-size of N=25 per group will provide adequate statistical power to test both our primary and secondary hypotheses.

Investigative Sequence and Timeline:

Year	Aims	Number of Studies (Total = 150)
1	1 and 2	~50 (~15-18 participants and 3 visits each)
2	1 and 2	~50 (~15-18 participants and 3 visits each)
3	1 and 2	~50 (~15-18 participants and 3 visits each)

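### As written, the primary Aim 1 comparison has no place for a woman tested at baseline and 6 months but not at 12 months, so it defaults to a 12-month completer analysis

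*Combined protocol and SAP*

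**What the plan says.** All references are to the combined protocol and SAP.

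- **Principle** (Statistics): "For all aims, the primary analyses will be performed using intention to treat with" the estradiol dosing regimen as the treatment group variable.
- **Time point**: the Power calculation paragraph states "The analysis of the 12 month outcomes will be considered the primary analysis". The 6-month results have a secondary role, described as "analyses of the earlier time point used to supplement the primary findings".
- **Aims 1 and 3** (Statistical Analysis): cluster analysis and regression, then "We will also perform a multivariable regression analysis taking into account all the covariates and applying penalized methods"; the lasso is the named example. No repeated-measures term appears.
- **Aim 2** (Statistical Analysis): "We will then fit a mixed-effects model with two fixed effects parameters, the intercept and the slope of the linear trend for the population", plus a random intercept and slope for each participant.
- **6-month visit**: the section Post-operative Study Visit at 6 Months states "The same protocol will be followed as the baseline study day protocol above except we will not check glucose, lipids and insulin levels"; the DXA scan is also left out. Tonometry, handgrip and cold pressor are therefore measured at 6 months.
- **Incomplete follow-up is foreseen** (Participant Retention): "Amounts will be prorated according to the visits the participant completes".

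The document gives no dropout rate, imputation rule, missing-data assumption, definition of analysis sets or sensitivity analysis.

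**The concern.** Intention to treat settles which arm a woman is counted in. It does not supply a 12-month value that she does not have. A regression on the 12-month outcome uses only women with that outcome, so without a missing-data method the primary Aim 1 comparison rests on 12-month completers. For the cardiovascular measures, a woman who leaves after month 6 has already given a result that is informative about her 12-month value, and the primary analysis as described does not draw on it.

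The trial is open-label, so reasons for leaving can differ by arm. If leaving is related to the 6-month result and the relation differs between arms, the completer contrast is biased. The bias can go either way: the difference is understated if poor responders leave the standard arm and overstated if they leave the titrated arm.

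**Working it through.** **1. The plan's own figure.** Inputs from the sample-size paragraph: 25 per group, difference 0.75 SD, one-tailed alpha 0.05, stated power 82%. Noncentrality is 0.75 × √(25/2) = 2.65 on 48 df, giving power of 83.4% (84.3% by normal approximation). The stated figure is reproduced to within 2 points. It needs a 12-month value from all 50 women, and 50 is also the planned accrual, so there is no allowance for loss.

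**2. Power with loss after month 6.** The loss fraction d and the 6-to-12-month correlation r are not in the document; both are assumptions. Completers per arm: 25(1−d). With the 6-month value used, the variance of an arm's 12-month mean is SD² × [(1−r²)/(25(1−d)) + r²/25], and the effective n is SD² divided by that variance. Power is from the same one-sided t-test.

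| d | Completers per arm | Completer power | Power using 6-month value, r = 0.3 | r = 0.5 | r = 0.7 |
|---|---|---|---|---|---|
| 10% | 22.5 | 79.7% | 80.0% | 80.6% | 81.5% |
| 20% | 20 | 75.3% | 76.0% | 77.2% | 79.2% |
| 30% | 17.5 | 70.1% | 71.2% | 73.2% | 76.3% |

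Once baseline is in the model, r is the correlation given baseline. If all pairs of visits correlate at ρ, this is ρ/(1+ρ): 0.33 for ρ = 0.5 and 0.41 for ρ = 0.7. The ratio of the two variances is 1 − d·r². At d = 25% that is 1 − 0.25 × 0.111 = 0.97 and 1 − 0.25 × 0.170 = 0.96. Simulation under random loss gave 0.976 and 0.960. The gain in precision is therefore only 2-4% of variance. The reason to change is protection against bias.

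**3. Bias under selective loss.** Assumed setting: 25 per arm, true difference 0.75 SD, baseline-adjusted regression, about 25-30% lost after month 6, with standard-arm loss concentrated among women with poor 6-month values. Simulations differing in the exact strength of selection gave these averages:

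| ρ | Completer regression | Using the 6-month value |
|---|---|---|
| 0.5 | 0.68-0.69 SD | 0.75 SD |
| 0.7 | 0.69-0.70 SD | 0.75 SD |

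The shortfall is about 0.05-0.07 SD.

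**4. Extreme case as a check.** Suppose exactly the worst 20% at month 6 leave one arm. Without baseline adjustment the completer mean in that arm shifts by r × φ(0.842)/0.8 = r × 0.35. That is 0.175 SD for r = 0.5 and 0.245 SD for r = 0.7, leaving 0.58 or 0.51 of the 0.75 SD. If instead the worst 20% on the baseline-adjusted 6-month value leave, and the analysis adjusts for baseline, the shift is (ρ−ρ²)/√(1−ρ²) × 0.35. That is 0.289 × 0.35 or 0.294 × 0.35, about 0.10 SD in both cases. The 0.05-0.07 SD in step 3 lies plausibly below this.

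**5. Size against sampling error.** With 25 × 0.75 ≈ 19 completers per arm and baseline adjustment, the standard error of the difference is √(2/19) × √(1−ρ²): 0.28 SD for ρ = 0.5 and 0.23 SD for ρ = 0.7. Taking the shortfall at each ρ (0.06-0.07 and 0.05-0.06 SD), the bias is about a fifth to a quarter of a standard error.

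**6. Whether the Aim 2 model fills the gap.** Its two named fixed effects are an intercept and a time slope. With no arm or arm-by-visit term it cannot return a 12-month regimen difference, and it is tied to the question of estradiol level. This sits awkwardly with the Statistics section, which names regimen as the treatment variable for all aims.

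**The case against.** The strongest case against is that silence is being read as a rule. This is right as far as it goes: a reader might infer that the plan excludes women who withdraw, or discards their 6-month data. No sentence does either. No completer set is defined, imputation is not ruled out, and the 6-month data do have a supplementary role. What stands is narrower: the plan describes no way for these women to enter the primary comparison.

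A reader might also infer that the more frequent estradiol checks in the titrated arm will drive differential loss after month 6. The Surgery and dismissal section runs those checks only until the target level is reached, so the document does not show that the contact difference lasts into months 6-12. Nor does it say that women learn their cardiovascular results. If symptoms or side effects drive leaving, using the 6-month cardiovascular value may remove only part of the bias. Differential loss is possible here but not shown.

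Three further points are fair. The bias is small against sampling error and rests on assumed inputs. The trial is described as providing pilot data. And a mixed model does not deliver full intention to treat: randomisation is at hospital dismissal, so women lost before month 6 have no post-baseline value and stay out. These points limit the weight of the concern. They do not supply the missing method, and the better analysis needs no new data.

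**Conclusion.** The concern holds in this limited form: the stated methods lead by default to a 12-month completer analysis for Aim 1, although the declared principle is intention to treat and 6-month cardiovascular results will be available. If loss is unrelated to outcome there is no bias, and using the 6-month values lowers variance by only 2-4%. If roughly 25-30% are lost after month 6 and loss in one arm follows the 6-month value, the bias is about 0.05-0.07 SD on a true 0.75 SD, in a direction that depends on which arm loses its poor responders. Loss rate, correlation and mechanism are all assumptions. The document does not support saying that the trial will be materially biased, only that the plan has no protection if such loss occurs. The point is confined to the cardiovascular outcomes; DXA, lipids, glucose and insulin have no 6-month value to use. It is worth changing as a cheap improvement.

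**What to change.** - **Aim 1 cardiovascular outcomes measured at 6 and 12 months** (tonometry, handgrip, cold pressor): make the primary analysis a mixed model for repeated measures with arm, visit, arm-by-visit, baseline value and unstructured covariance. Include every randomised woman with any post-baseline value, in her assigned arm. Keep the 12-month arm difference as the primary contrast, and say how the lasso covariate selection relates to this model.
- **Assumption:** state that the model assumes data are missing at random given arm, baseline and 6-month values.
- **Losses:** report number, timing and reasons by arm, showing separately those before month 6, whom the model does not recover.
- **DXA and metabolic outcomes:** state that results cover 12-month completers.
- **Questionnaires:** none of the three aims names one as an outcome; they may use the same model as secondary outcomes.
- **Aim 2:** reconcile its list of fixed effects with the statement that regimen is the treatment variable for all aims.

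The cost is plan wording only, with no new visits or data. The downside is reliance on missing at random, which cannot be verified but is weaker than what an analysis of completers alone needs.
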